3.3. Benefit/Risk Assessment

More information about the known and expected benefits, risks, SAEs, and reasonably anticipated AEs of LY3074828 are to be found in the IB.

4. Objectives and Endpoints

Table AMAG.1 shows the objectives and endpoints of the study.

Table AMAG.1. Objectives and Endpoints

Objectives	Endpoints

Primary
 
 To test the hypothesis that treatment with LY3074828 is superior to placebo in the proportion of subjects with endoscopic response at Week 12, defined as 50% reduction from baseline in SES-CD Score 	
 Proportion of subjects achieving endoscopic response at Week 12

Secondary
 
 To evaluate the safety and tolerability of treatment with LY3074828 To evaluate the effect of LY3074828 on the proportion of subjects with endoscopic response at Week 52, defined as 50% reduction from baseline in SES-CD score To evaluate the efficacy of treatment with LY3074828 as superior to placebo in endoscopic remission (defined as an SES-CD score of <4 ileal-colonic or <2 for isolated ileal disease, and no subscore >1) at Week 12 To evaluate the effect of LY3074828 on the proportion of subjects with endoscopic remission (defined as an SES-CD score of <4 ileal-colonic or <2 for isolated ileal disease, and no subscore >1) at Week 52 To evaluate the efficacy of treatment with LY3074828 as superior to placebo in PRO remission (defined as SF \leq2.5 and AP \leq1) at Week 12 To evaluate the effect of LY3074828 on the proportion of subjects with PRO remission (defined as SF \leq2.5 and AP \leq1) at Week 52 To evaluate the effect of LY3074828 on health outcomes/quality-of-life measures (including: PGRS score, PGRC score, IBDQ score, SF-36 score, and FACIT-Fatigue) at Weeks 12 and 52 To characterize the PK of LY3074828 	
 AEs and discontinuation rates; mean change vital signs; laboratory values Proportion of subjects achieving endoscopic response at Week 52 Proportion of subjects achieving endoscopic remission at Week 12 Proportion of subjects achieving endoscopic remission at Week 52 Proportion of subjects achieving PRO remission at Week 12 Proportion of subjects achieving PRO remission at Week 52 The mean change from baseline for PGRS score, IBDQ score, FACIT-Fatigue, and SF-36, and the mean PGRC at Weeks 12 and 52 Clearance and volume of distribution

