 
reported using the BMC scale
	
all time points evaluated

Objectives	Endpoints

 • To evaluate the effect of LY3074828 on QIDS-SR16 at Weeks 12 and 52 • To explore the development of any anti-LY3074828 antibodies that are formed and their effect on safety, PK, and PD of LY3074828 • To evaluate changes in CDAI from baseline 	
 • Change from baseline in reported QIDS-SR16 score at Weeks 12 and 52 • Proportion of subjects who are ADA+. Proportion of ADA+ subjects who experience certain immunogenicity-specific AEs. PK/PD subgroup analyses on ADA+ subjects • Change from baseline in CDAI

 • To evaluate the elimination of neutrophils from the mucosa by histopathology at Week 52 	
 • Absence of lamina propria and epithelial neutrophils at Week 52 assessed by 
 ○ GHAS ○ RHI

Abbreviations: ADA = anti-drug antibodies; AE = adverse event; AP = abdominal pain; BMC = bowel movement count; CDAI = Crohn’s Disease Activity Index; **CCI** CRP = C-reactive protein; EC₅₀ = drug concentration that produces 50% of E_{max}; E_{max} = maximum effect; FACIT-Fatigue = Functional Assessment of Chronic Illness Therapy–Fatigue; FCP = fecal calprotectin; GHAS = Global Histologic Disease Activity Score; IBDQ = Inflammatory Bowel Disease Questionnaire; Pain NRS = Numeric Rating Scale; PD = pharmacodynamics; PK = pharmacokinetics; PGRC = Patient’s Global Rating of Change; PGRS = Patient’s Global Rating of Severity; PRO = patient-reported outcomes; PRO2 = Patient Reported Outcome2; QIDS-SR16 = Quick Inventory of Depressive Symptomatology–Self Report (16 Items); RHI = Robarts Histologic Index; SES-CD = Simple Endoscopic Score for Crohn’s Disease; SF = stool frequency; SF-36 = Medical Outcomes 36-Item Short Form Health Survey.

5. Study Design

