- [23] have an abnormality in the 12-lead ECG that, in the opinion of the investigator, increases the risks associated with participating in the study
- [24] increases the risks associated with participating in the study if the presence or history within 12 months prior to screening of significant uncontrolled cerebrocardiovascular (for example, myocardial infarction, unstable angina, unstable arterial hypertension, moderate-to-severe heart failure [New York Heart Association class III/IV], or cerebrovascular accident); presence of respiratory, hepatic, renal, gastrointestinal, endocrine, hematologic, or abnormal laboratory values at screening that, in the opinion of the investigator, pose an unacceptable risk to the subject if participating in the study or of interfering with the interpretation of data

- [25] presence of significant uncontrolled neuropsychiatric disorder, have history of a suicide attempt or have a score of 3 on Item 12 (Thoughts of Death or Suicide) of the Quick Inventory of Depressive Symptomatology–Self Report (16 Items) (QIDS-SR16) at screening (Visit 1) or baseline (Week 0; Visit 2)
- [26] are investigator site personnel directly affiliated with this study and/or their immediate families. Immediate family is defined as a spouse, parent, child, or sibling, whether biological or legally adopted.
- [27] are Lilly employees or employees of third-party organizations (TPOs) involved with the study
- [28] are currently enrolled in a clinical trial involving an investigational product or nonapproved use of a drug or device, OR are concurrently enrolled in any other type of medical research not scientifically or medically compatible with this study, per investigator judgment
- [29] have previously completed or withdrawn from this study or any other study investigating LY3074828. This criterion does not apply to subjects undergoing rescreening procedures.
- [30] have received live, attenuated vaccine(s) within 2 months of screening or intend to receive such during the study; vaccines should be avoided for 2 months after the last dose of study drug. Uses of nonlive (inactivated) vaccinations are allowed for all subjects.
- [31] have human immunodeficiency virus/acquired immune deficiency syndrome (HIV/AIDS) or test positive for antibodies at screening

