9.3. Adverse Events

Investigators are responsible for monitoring the safety of subjects who have entered this study and for alerting Lilly or its designee to any event that seems unusual, even if this event may be considered an unanticipated benefit to the subject.

The investigator is responsible for the appropriate medical care of subjects during the study.

Investigators must document their review of each laboratory safety report.

The investigator remains responsible for following, through an appropriate health care option, AEs that are serious or otherwise medically important, considered related to the investigational product or the study, or that caused the subject to discontinue the investigational product before completing the study. The subject should be followed until the event resolves, stabilizes with appropriate diagnostic evaluation, or is reasonably explained. The frequency of follow-up evaluations of the AE is left to the discretion of the investigator.

Lack of drug effect is not an AE in clinical studies, because the purpose of the clinical study is to establish treatment effect.

After the ICF is signed, study site personnel will record via electronic case report form (eCRF) the occurrence and nature of each subject's preexisting conditions, including clinically significant signs and symptoms of the disease under treatment in the study. In addition, site personnel will record any change in the condition(s) and any new conditions as AEs. Investigators should record their assessment of the potential relatedness of each AE to protocol procedure, investigational product, via eCRF.

The investigator will interpret and document whether or not an AE has a reasonable possibility of being related to study treatment, study device, or a study procedure, taking into account the disease, concomitant treatment or pathologies.

A “reasonable possibility” means that there is a cause and effect relationship between the investigational product, study device and/or study procedure and the AE.

The investigator answers yes/no when making this assessment.

Planned surgeries and nonsurgical interventions should not be reported as AEs unless the underlying medical condition has worsened during the course of the study.

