Safety Population Period 2 [Weeks 12-52]	2.1) Treatment-Emergent Adverse Events	An event ongoing at the time of the first dose of Period 2 study treatment. If time is not collected for an event starting on Visit 8 dose date, it will be assumed that it occurred after first dose.	Period 2 (Weeks 12-52): starts at Period 2 Start Date and ends at Period 2 End Date or the day of the study treatment disposition visit (whichever is earliest) unless otherwise noted.
	2.2) Treatment-Emergent Abnormal Labs and Vital Signs	The last non-missing assessment (scheduled or unscheduled) recorded prior to the first dose of Period 2 study treatment. If time is not collected for a measurement taken on Visit 8 dose date, it will be assumed that it occurred prior to first dose.	Period 2 will be defined as above (2.1). All scheduled and unscheduled measurements will be included.
	2.3) Change from Last Baseline to Week xx and to Last Postbaseline for Labs and Vital Signs	The last non-missing scheduled assessment recorded prior to the first dose of Period 2 study treatment. If time is not collected for a measurement taken on Visit 8 dose date, it will be assumed that it occurred prior to first dose.	Period 2 will be defined as above (2.1). Only scheduled visits will be included. The ETVs are considered scheduled visits.
Safety population All SC LY [All treatment periods where LY SC is administered]	3.1) Treatment-Emergent Adverse Events	An ongoing event at the time of the first dose of LY SC treatment. If time is not collected for an event starting on the first dose date, it will be assumed that it occurred after first dose.	LY SC Treatment Period: starts at the administration of the first dose of LY SC treatment and ends at the study treatment disposition visit (ie, the last visit at which the LY SC treatment was administered).
	3.2) Treatment-Emergent Abnormal Labs and Vital Signs	The last non-missing assessment (scheduled or unscheduled) recorded prior to the first dose of LY SC treatment. If time is not collected for a measurement taken on first dose date, it will be assumed that it occurred prior to first dose.	LY SC Treatment Period will be defined as above (3.1). All scheduled and unscheduled measurements will be included.

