QIDS-SR16	
The QIDS-SR16 is a self-administered 16-item instrument intended to assess the existence and severity of symptoms of depression as listed in the American Psychiatric Association’s Diagnostic and Statistical Manual of Mental Disorders, 4th Edition (DSM-IV) (APA 1994). A patient is asked to consider each statement as it relates to the way they have felt for the past 7 days. There is a 4-point scale for each item ranging from 0 to 3. The 16 items corresponding to 9 depression domains are summed to give a single score ranging from 0 to 27, with higher scores denoting greater symptom severity. The domains assessed by the instrument include: 1) sad mood, 2) concentration, 3) self-criticism, 4) suicidal ideation, 5) interest, 6) energy/fatigue, 7) sleep disturbance (initial, middle, and late insomnia or hypersomnia), 8) decrease/increase in appetite/weight, and 9) psychomotor agitation/retardation. Additional information and the QIDS-SR16 questions may be found at the University of Pittsburgh IDS/QIDS internet page [www.http://www.ids-qids.org/].
 
QIDS-SR16 is assessed Weeks -4, 0, 11-12, 52, 104, and 120 during Screening, Periods 1, 2, 3, and Follow-Up.
	QIDS-SR16 total score	The algorithm for scoring the QIDS-SR16 is found in Appendix 5 .

Description and Derivation of Health Outcomes Endpoints Except CDAI

Measure	Description / Timing	Variable	Derivation / Comment
CCI			

CCI Therapy-Fatigue; IBD = inflammatory bowel disease; IBDQ = Inflammatory Bowel Disease Questionnaire; MCS = mental component summary; CCI
CCI PCS = physical component summary; PGRC = Patient's Global Rating of Change; PGRS = Patient's Global Rating of Severity; QIDS-SR16 = Quick Inventory of Depressive Symptomatology-Self Report (16 Items); SF-36 = 36-Item Short Form Health Survey.

Table AMAG.6.11. Description of Health Outcomes Analyses

Measure	Variable	Analysis Method (Section 6.1.6)	Population (Table AMAG.6.1)	
PGRS	Mean PGRS score	Primary Analysis: MMRM – change from baseline	ITT Population	
		Sensitivity Analysis: ANCOVA (mBOCF) – change from baseline	ITT Population	
		Descriptive statistics – observed values	EHO Group 2	
PGRC	PGRC score	Descriptive statistics – observed values	ITT Population, EHO Group 2	
IBDQ	IBDQ score	Primary Analysis: MMRM – change from baseline	ITT Population	
		Sensitivity Analysis: ANCOVA (mBOCF) – change from baseline	ITT Population	
		Descriptive statistics – observed values	EHO Group 2	

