	IBDQ Responder	Primary Analysis: Logistic regression analysis with NRI	ITT Population	
		Descriptive statistics with NRI	EHO Group 2	
FACIT- Fatigue	FACIT-Fatigue Total score	MMRM – change from baseline	ITT Population	
		Descriptive statistics – observed values	EHO Group 2	
	FACIT-Fatigue Responder	Primary Analysis: Logistic regression analysis with NRI	ITT Population	
		Descriptive statistics with NRI	EHO Group 2	
SF-36 Version 2	SF-36 Domain Scores: 
 • physical functioning • role-physical • role-emotional • bodily pain • vitality • social functioning • mental health • general health SF-36 physical component score SF-36 mental component score	MMRM – change from baseline	ITT Population	
		Descriptive statistics – observed values	EHO Group 2	

[figure not shown]
Measure	Variable	Analysis Method (Section 6.1.6)	Population (Table AMAG.6.1)	
	SF-36 PCS Responder SF-36 MCS Responder	Primary Analysis: Logistic regression analysis with NRI	ITT Population	
		Descriptive statistics with NRI	EHO Group 2	

BMC	Mean BMC score	Primary Analysis: MMRM – change from baseline	ITT Population	
		Sensitivity Analysis: ANCOVA (mBOCF) – change from baseline	ITT Population	
		Descriptive statistics – observed values	EHO Group 2	
		Additional exploratory/psychometric analyses will be described in a separate health outcomes SAP; these analyses will be conducted by Lilly GPORWE.		
QIDS-SR16	QIDS-SR16 total score	MMRM – change from baseline	ITT Population	
		Descriptive statistics – observed values	EHO Group 2	

Abbreviations: ANCOVA = analysis of covariance; BMC = bowel movement count; CCI [redacted]; EHO = efficacy and health outcomes; FACIT-Fatigue = Functional Assessment of Chronic Illness Therapy–Fatigue; GPORWE = Global Patient Outcomes and Real World Evidence; IBDQ = Inflammatory Bowel Disease Questionnaire; ITT = intent-to-treat; mBOCF = modified baseline observation carried forward; MMRM = mixed model for repeated measures; CCI [redacted]; PGRC = Patient’s Global Rating of Change; PGRS = Patient’s Global Rating of Severity; QIDS-SR16 = Quick Inventory of Depressive Symptomatology–Self Report (16 Items); SAP = statistical analysis plan; SF-36 = 36-Item Short Form Health Survey.

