Appendix 5. Algorithm for Calculating the QIDS-SR16 Total Score

The Quick Inventory of Depressive Symptomatology-Self Report (16 Items) (QIDS-SR16) is a 16-item self-report instrument intended to assess the existence and severity of symptoms of depression (Rush et al. 2003). The following table can be used to calculate the total score.

Enter the highest score recorded for the 4 sleep items (items 1 to 4)	_____
Enter score for item 5	_____
Enter the highest score recorded for the appetite/weight items (items 6 to 9)	_____
Enter score for item 10	_____
Enter score for item 11	_____
Enter score for item 12	_____
Enter score for item 13	_____
Enter score for item 14	_____
Enter the highest score recorded for the psychomotor items (items 15 and 16)	_____
Sum the scores to obtain a total score (Total score range 0 – 27)	_____

If any of the 9 items above are missing, the QIDS-SR16 total score will be considered missing.

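### The visible SAP analyses QIDS-SR16 only as a total score, so new suicidal ideation marked on Item 12 but not recorded as an adverse event is not counted as ideation in any visible table or listing

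*SAP*

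**What the plan says.** - **Entry.** Protocol 6.2, criterion [25], excludes subjects who "have a score of 3 on Item 12 (Thoughts of Death or Suicide) of the Quick Inventory" at Visit 1 or Visit 2. The criterion also covers a past suicide attempt and significant uncontrolled neuropsychiatric disorder.
- **Collection.** SAP Table AMAG.6.10: "QIDS-SR16 is assessed Weeks -4, 0, 11-12, 52, 104, and 120 during Screening, Periods 1, 2, 3, and Follow-Up". The protocol's Schedule of Activities places the last of these at Visit 804 or early termination.
- **Endpoint.** Protocol Table AMAG.1 lists QIDS-SR16 as exploratory: "Change from baseline in reported QIDS-SR16 score at Weeks 12 and 52". The safety endpoints in the same table are "AEs and discontinuation rates; mean change vital signs; laboratory values".
- **Analysis.** SAP Tables AMAG.6.10 and AMAG.6.11 define a single variable, the "QIDS-SR16 total score", with MMRM change from baseline in ITT and observed values in EHO Group 2.
- **Scoring.** In SAP Appendix 5, Item 12 is one line of the sum. The missing-data rule is: "If any of the 9 items above are missing, the QIDS-SR16 total score will be considered missing".
- **Dimension scores.** Protocol 10.3.3.3 names QIDS-SR16 among the questionnaires whose dimension sub-totals are to be summarised as group means with 90% CIs, where that is appropriate. The SAP's QIDS-SR16 rows do not take this up.
- **Safety topics.** The visible parts of SAP 6.14.8 cover hepatic tests, infections, hypersensitivity and injection site reactions.
- **Adverse events.** Protocol 9.3 says that "site personnel will record any change in the condition(s) and any new conditions as AEs". SAP 6.14.2 tabulates these by preferred term.

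**The concern.** The protocol treats a single answer on Item 12 as serious enough to keep a person out of the trial. The same answer after dosing has no individual-level output in the visible SAP. Apart from enrolment deviations, every later score of 3 is new relative to the Visit 1-2 baseline, so it is easy to define and count.

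Ideation reaches the safety tables only if a site turns the questionnaire answer into an adverse event. If it does not, the answer survives only inside a total, where improvement in another domain can cancel it. At stake is a plain count by arm of subjects who newly marked the item, on a form that the trial already collects.

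**Working it through.** **1. The plan's own figure.** Appendix 5 sums nine components, each scored 0 to 3: 9 × 3 = 27. This reproduces the stated range of 0 to 27.

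**2. What the total can show.** A subject going from 0 to 3 on Item 12 adds 3 points. A fall in the sleep component from 3 to 0 cancels that exactly. At group level the shift in the mean is 3k/n for k such subjects out of n. Allocation of 180 at 2:1:1:2 gives about 60, 30, 30 and 60 per arm.
- One subject of 60: 3/60 = 0.05 points.
- Two subjects of 60: 6/60 = 0.10 points.
- One subject of 30: 3/30 = 0.10 points.

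Neither the MMRM nor the descriptive means can therefore show new ideation as ideation. If another component is unanswered, the total is missing even though Item 12 was answered.

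**3. Who falls outside the Week 52 summary.** SAP Table AMAG.6.1 excludes from EHO Group 2 the subjects who stop treatment in Period 1 but stay in the study. The same note says that their data will be reviewed if that is judged necessary. Their Week 52 total is thus outside the planned summary, with review left to discretion.

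**4. Illustration of how often this could arise.** The documents give no rates. Assume complete Week 12 forms, a probability p of newly reaching 3, and a share c of those cases also recorded as adverse events. An uncounted case then has probability p(1 − c). Among the 120 subjects on LY3074828 (60 + 30 + 30), the chance of at least one is 1 − [1 − p(1 − c)]^120:

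| Share recorded as AE (c) | p = 1% | p = 2% | p = 3% |
|---|---|---|---|
| 0 (upper bound) | 70% | 91% | 97% |
| 50% | 45% | 70% | 84% |
| 80% | 21% | 38% | 51% |
| 90% | 11% | 21% | 30% |

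The expected number is 120 × p × (1 − c). It runs from 120 × 0.01 × 0.1 = 0.12 to 120 × 0.03 × 0.5 = 1.8 subjects for c between 50% and 90%. These figures concern scores of 3 only; increases to 1 or 2 are not included.

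**5. What a zero would say.** With no events in n subjects, the one-sided 95% upper limit is 1 − 0.05^(1/n): 2.5% for 0 of 120 on drug and 4.9% for 0 of 60 on placebo.

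**The case against.** The best case for leaving the plan alone has several parts.

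- **The SAP matches the protocol.** QIDS-SR16 is an exploratory change-in-score endpoint under health outcomes, and no visible text makes suicidality a safety endpoint. This stands. A reader might infer a breach of the protocol, but the documents do not support that. An entry exclusion does not by itself create a later reporting duty.
- **Other routes exist.** New conditions must be recorded as adverse events. Protocol 10.3.7 provides for ongoing blinded safety review under a separate plan, and SAP 6.1 allows further exploratory analyses. These narrow the gap, and it would be wrong to infer that ideation in this trial goes unreported. None of them prespecifies a count of new Item 12 cases.
- **Protocol 10.3.3.3 could yield a mean for the ideation domain.** It is conditional and absent from the SAP's QIDS-SR16 rows, and a mean does not count cases.
- **The baseline is already right.** A reader might infer from SAP Table AMAG.6.4 that a rise at Week 12 persisting to Week 52 would count as no change, because its Period 2 baseline for treatment-emergent abnormal labs and vital signs is "The last non-missing assessment (scheduled or unscheduled) recorded prior to the first dose of Period 2 study treatment". That table does not govern QIDS-SR16. Table AMAG.6.3 sets the Study Baseline for all health outcomes analyses, including EHO Groups 2 and 3. The problem would arise only if a new Item 12 table were put in the safety section under that section's rules.
- **Redaction.** Sections next to 6.11 and after 6.14.8.4 are blacked out, and adverse events of special interest are mentioned without a visible definition. An Item 12 output may exist there.
- **The yield is small.** The item is a single one with 7-day recall, there is essentially one placebo-controlled reading, and a zero on placebo leaves an upper limit of 4.9%, above every p assumed. This stands as a limit on what the table can show, and it rules out a formal comparison.

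**Conclusion.** The point holds as a minor safety-reporting improvement, limited to the visible text. As written there, the plan reports the mean total and whatever ideation is recorded as adverse events. It does not report how many subjects per arm newly marked Item 12. There is no contradiction between the documents and no effect on alpha, power or the primary endpoint.

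The dilution result (0.10 points for two of 60) follows from the scoring rule and the allocation. The probabilities of 11% to 97% rest wholly on assumed rates. A reader might take them as evidence that cases are likely to be missed; they only illustrate a range, and the true number is unknown.

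**What to change.** Add to SAP 6.14.8:

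1. **A descriptive table by treatment** for Safety Population Period 1, with descriptive summaries for Period 2 and for All LY including Follow-Up. Give the number and percentage of subjects whose maximum postbaseline Item 12 score exceeds their maximum at Visits 1-2, and the number and percentage reaching 3. State that the Study Baseline of Table AMAG.6.3 applies even though the table sits in the safety section.
2. **One listing** of every treated subject with a postbaseline Item 12 score of 3, including those who stopped treatment and stayed in the study. Show visit, treatment and any matching adverse event. Include the Week 12 score, so that a rise already present then can be told from a later one.
3. **A data rule:** use every answered Item 12, even when the total is missing.

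The cost is SAP wording and slight extra programming on data already collected. The output is a noisy single item with essentially one placebo-controlled reading (Week 11-12). It should be presented without formal testing, as a supplement to adverse event reporting and not a replacement. If a redacted section already contains it, the sponsor need only confirm that.
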